16.3 Analysis of PK parameters

Summary statistics of plasma concentration table: For each time point summary statistics (N, arithmetic mean, standard deviation (SD), minimum, median, maximum) of the analyte concentration by treatment group, visit and time point will be presented.

PK metrics: For each patient PK metrics will be tabulated (see cf. table 2). In the same tabulation for each treatment group PK metrics will be summarized using n, arithmetic mean, standard deviation (SD), minimum, median, maximum. Presentation of results will be by visit, treatment group and total.

Figures:

1. Mean concentrations versus nominal time by treatment group using the original (untransformed) scale of concentrations. The curves of each visit and each treatment group will be put into one graph, having an overlay plot in the end with two curves for each treatment group.
2. Individual analyte concentrations versus nominal time curves using the original concentration scale.

16.4 Analysis of PD parameters

The same tabulations and figures will be prepared for the glucagon plasma concentrations and PD metrics.

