Administration of dasiglucagon may be associated with a risk of allergic reactions similar to those observed for other therapeutic peptides or proteins. Patients with known or suspected allergies to the trial medications or related products will be excluded from the trial. Mild or moderate allergic reactions may include symptoms of rash, fever, flu-like symptoms, nausea, headache, and myalgia. Acute generalized hypersensitivity reactions are usually very rare but may include symptoms of flushing, sweating, dizziness, change in blood pressure and difficulties in breathing. No severe acute hypersensitivity reactions have been observed in the 3 clinical trials conducted with dasiglucagon. Direct access to resuscitation equipment is ensured at the clinical trial sites.

With the exception of medical examinations, a patient participating in this trial is not likely to derive any personal health-related benefits. The results of the trial may contribute to the future use of dasiglucagon in patients with diabetes mellitus experiencing severe hypoglycemic reactions.

Overall, the benefit to risk ratio for patients entering the ZP4207-16136 trial is considered acceptable.

6. Trial objectives

Primary objective

- To evaluate the immunogenicity of repeated single doses of dasiglucagon and GlucaGen following s.c. administration in T1DM patients.

Secondary objective

- To evaluate the safety, tolerability and pharmacodynamic response of repeated single doses of dasiglucagon following s.c. administration compared with s.c. GlucaGen in T1DM patients.

Primary endpoint:

- Overall ADA incidence
This will be calculated as a percentage of the combined results of treatment-induced ADA-positive patients and treatment-boosted ADA-positive patients and the total number of evaluable patients, excluding baseline-positive patients without any samples available after drug administration.

Key secondary endpoints:

- Treatment-induced ADA
Incidence calculated as a percentage of the total number of evaluable patients that were ADA negative at baseline and ADA positive after drug administration and the total number of evaluable patients, excluding baseline positive patients without any samples available after drug administration.
- Treatment-boosted ADA

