7.4.2 Treatments administered

Dasiglucagon is a stable peptide analog of human glucagon in a ready-to-use liquid formulation indicated for treatment of severe hypoglycemia in insulin dependent patients with diabetes mellitus. Dasiglucagon is in clinical development and has no marketing authorization as yet. GlucaGen is approved in the EU and US and is indicated for treatment of severe hypoglycemic reactions, which may occur in the management of insulin-treated children and adults with diabetes mellitus.

Patients in this trial have not previously been treated with dasiglucagon (ZP4207) and will be randomly assigned (1:1) to receive 1 of the following trial medications:

- 0.6 mg dasiglucagon
- 1 mg GlucaGen

Prior to administration of trial medication at all dosing visits patients must reach a target plasma glucose level of 70-150 mg/dL. If the patient presents with plasma glucose > 150 mg/dL, corrective amounts of fast acting insulin will be administered at the investigator's discretion. Plasma glucose measured after 20 and after 40 minutes should ensure that the patient has reached the targeted 70-150 mg/dL. If the patient presents with plasma glucose < 70 mg/dL glucose ingestion will be provided in order to reach target plasma glucose of 70-150 mg/dL documented by plasma glucose measurements after 20 and 40 minutes, respectively.

Following the first (Visit 2) and third (Visit 4) dose administration, patients must be fasting for 90 min after dosing. Following the 90-min blood sample draw after the administration of the first (Visit 2) and third (Visit 4) dose administration, patients may be treated individually in order to alleviate any potential side effects in order to minimize premature treatment discontinuation and consequently reduce the amount of missing data. This treatment can also be instituted immediately after the second dose administration (Visit 3), as pharmacodynamics will not be assessed at this visit.

In order to minimize the number of patients discontinuing treatment prematurely and consequently reduce the amount of missing data, the following treatment modalities may be used, as considered appropriate by the investigator:

At visit 2 and 4:

- 90 min after dosing patients will be allowed to eat and drink moderately to make them feel comfortable
- 90 min after dosing a moderate and individualized corrective dose of insulin to convert the induced hyperglycemia to euglycemia, after agreement with the investigator

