7.6.3 Pharmacodynamic measurements

The plasma glucose profile will be assessed based on plasma concentration data ($AUE_{0-30\text{min}}$, $AUE_{0-90\text{min}}$, CE_{max} , t_{max}) from samples collected at dosing Visits 2 and 4 (first and third dosing visit).

Samples will be collected pre-dose, and at 5, 10, 30, 60, and 90 min post-dosing. The actual time of blood sampling for evaluation of plasma glucose should not deviate from the nominal time by more than ± 1 min. Pre-dose is defined as within 5 min prior to dosing.

The samples will be sent to the clinical laboratory and analyzed using a sensitive and validated assay for glucose measurements.

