3. STUDY OBJECTIVES

The present trial aims to evaluate that immunogenicity risk with an assessment of the occurrence of ADAs and neutralizing ADAs, and of cross-reactivity with native glucagon, following repeated single doses of dasiglucagon by s.c. administration in T1DM patients. The trial further aims to evaluate the pharmacodynamics and pharmacokinetic responses and to correlate the consequence of an antibody response, if any, to pharmacodynamic and pharmacokinetic endpoints. The reference product in this trial is GlucaGen®, a recombinant human glucagon approved for the treatment of the severe hypoglycemic reactions that may occur in the management of insulin-treated children and adults with diabetes mellitus.

Primary objective

The primary objective is to describe the immunogenicity of repeated single doses of dasiglucagon and GlucaGen® following s.c. administration in T1DM patients.

Secondary objectives

The secondary objective consists of analyzing the safety, tolerability and pharmacodynamic response of repeated single doses of dasiglucagon following s.c. administration compared with s.c. GlucaGen® in T1DM patients.

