11.4 Adjustment for covariates

N/A.

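### The glucose response is to be compared with GlucaGen, but the SAP plans no between-arm difference, no confidence interval and no adjustment for pre-dose glucose

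*SAP*

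**What the plan says.** - **Objective.** Protocol section 6 gives the secondary objective as "To evaluate the safety, tolerability and pharmacodynamic response of repeated single doses of dasiglucagon following s.c. administration compared with s.c. GlucaGen" in T1DM patients. SAP section 3 carries the same aim: "pharmacodynamic response of repeated single doses of dasiglucagon following s.c. administration compared with s.c. GlucaGen". Amendment 2 (section 3.2) added the responder endpoint, a rise of at least 20 mg/dL within 30 minutes, to help bridge to the pivotal efficacy trial; the same amendment added the PD part of the objective.
- **Analysis.** SAP 16.4 reads, in full: "The same tabulations and figures will be prepared for the glucagon plasma concentrations and PD metrics". The word glucagon there appears to be a slip for glucose, since Table 14.4.2.1 in SAP Appendix C is for plasma glucose. The tabulations meant are those of SAP 16.3, where "for each treatment group PK metrics will be summarized using n, arithmetic mean, standard deviation (SD), minimum, median, maximum", by visit and with a total, plus mean and individual curves. The PKMETRIC shell in Appendix D, to be adapted for PD, has no contrast column. SAP section 6 allows confidence intervals where the relevant section indicates them; 16.3 and 16.4 indicate none.
- **Metrics.** SAP 16.1 (Table 3) defines CEmax as a change from baseline and AUE as baseline-adjusted. It derives Inc20 as yes when raw glucose at 30 minutes has reached 20 mg/dL. SAP 16.2, in its list for determining PK and PD metrics, sets every pre-dose concentration to zero.
- **Data.** Before dosing, "patients must reach a target plasma glucose level of 70-150 mg/dL" (Protocol 7.4.2). Glucose samples are "analyzed using a sensitive and validated assay for glucose measurements" (Protocol 7.6.3), with no distinction by arm.
- **Contrast elsewhere.** SAP section 5 declines a formal comparison because the ADA assays are arm-specific. Protocol 10.1.3, SAP 12.1 and the ENDPOINT shell nevertheless give the ADA incidence difference a 95% interval.

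**The concern.** A comparative objective needs a comparative estimate. Here the reader gets two columns of summaries and must judge by eye how far apart the products are and how uncertain that gap is. The plan puts an interval on the contrast whose assays it calls not comparable, and none on the contrast measured with one assay in both arms.

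Pre-dose glucose matters because patients may be dosed anywhere in an 80 mg/dL range. Subtracting the baseline, as CEmax and AUE do, does not remove dependence on it. If the size of the rise varies with the starting level, a chance difference in starting level between arms carries into the difference in change. The covariate is already measured at Visits 2 and 4, so adjusting for it costs nothing in data.

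**Working it through.** **1. The plan's own figure.** No sample size, SD, margin or power is stated for any glucose endpoint. The 45 per arm comes from ADA: ln(0.10)/ln(0.95) = 44.9, rounded up to 45; the one-sided 90% upper bound with no events is 1 − 0.10^(1/45) = 0.0499. It reproduces. I use it only as the number per arm.

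**2. Unadjusted difference.** 95% half-width = t(0.975, 2n − 2) × SD × √(2/n).
- n = 45: 1.987 × √(2/45) = 0.419 SD.
- n = 56 (112/2, all randomized): 0.375 SD. The PK/PD set in SAP section 8 asks only for one pre- and post-dose PK value at one visit, so n may lie between the two.
- For CEmax with an assumed SD of 20, 30 or 40 mg/dL and n = 45: 8.4, 12.6 or 16.8 mg/dL.

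**3. With pre-dose glucose as covariate.** Multiply by √(1 − r²). For assumed r = 0.3 the factor is 0.954 (about 5% narrower, 0.40 SD); for r = 0.6 it is 0.80 (20% narrower, 0.34 SD).

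**4. Chance imbalance in pre-dose glucose.** If values are assumed uniform over 70 to 150 mg/dL, the SD is 80/√12 = 23.1. The SE of the arm difference is 23.1 × √(2/45) = 4.87, so the 95% range is ±1.96 × 4.87 = ±9.5 mg/dL. Its effect on the CEmax difference is already part of the unadjusted half-width in step 2; it is not an extra error.

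**5. Responder difference, Newcombe 95% interval, 45 per arm.**

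| Dasiglucagon | GlucaGen | Difference (points) | 95% CI |
|---|---|---|---|
| 45/45 | 45/45 | 0 | −7.9 to +7.9 |
| 44/45 | 45/45 | −2.2 | −11.6 to +5.9 |
| 43/45 | 45/45 | −4.4 | −14.8 to +4.1 |

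**6. What the SAP 16.2 zero rule would do to glucose.** With measured pre-dose value B replaced by 0, and linear trapezoids on the 0, 5, 10, 30, 60 and 90 minute samples:
- CEmax becomes the raw maximum, inflated by B: 70 to 150 mg/dL.
- AUE0-30 is inflated by (30 − 2.5) × B = 27.5B: 1925 to 4125 mg·min/dL.
- AUE0-90 is inflated by (90 − 2.5) × B = 87.5B: 6125 to 13125 mg·min/dL.
- The pre-dose covariate is 0 for everyone, so the adjustment in step 3 cannot be fitted.

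**7. Inc20 as derived in SAP 16.1.** A patient dosed at 70 to 150 mg/dL already exceeds 20 mg/dL before any response. Taken literally, a patient whose glucose does not move scores yes, and the difference in step 5 would be close to zero by construction.

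**The case against.** The strongest reply is that the trial is descriptive by design. Protocol 10.1.1 makes all analysis descriptive, and Amendment 2 says the PD endpoints, including the responder, will be summarized descriptively. The same objective sentence covers safety and tolerability, which are also tabulated by arm without contrasts, so side-by-side description is a possible reading. That stands as an explanation of the SAP. It does not rule out an estimate with an interval: Protocol 10.1.1 excludes tests, and the plan itself reports an ADA difference with a CI under the same rule.

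Several stronger readings are tempting and are not supported:
- *Pre-dose glucose is ignored.* It is not. CEmax and both AUEs are defined relative to baseline. What is missing is covariate adjustment.
- *SAP 11.4 rules out covariates for PD.* Its "Adjustment for covariates" entry of N/A belongs to the immunogenicity section and does not govern sections 15 and 16, which are simply silent.
- *The yes/no responder will be summarized by mean and SD.* SAP section 6 already provides counts and percentages for categorical variables, and the shell is to be adapted. Only the difference and its interval are absent.
- *The trial could not say how close the products are.* An unadjusted difference and CI can be computed from the planned n, mean and SD. The plan does not present them, and a reader cannot get the adjusted version from the summary tables.

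**Conclusion.** The point holds in this form: a stated secondary objective compares the glucose response with GlucaGen, and no planned output estimates that comparison or its uncertainty. The one reason given against comparing arms concerns ADA assays and does not reach glucose. Pre-dose glucose is used in the metrics but not adjusted for.

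At 45 per arm the planned data would support a 95% interval of about ±0.42 SD. The mg/dL figures rest on an assumed SD of 20 to 40 and the 5 to 20% gain on an assumed correlation of 0.3 to 0.6, neither of which is in the documents. The omission does not depend on them.

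The primary ADA analysis is unaffected. This is a change that should be made, not a flaw that invalidates the trial. The two derivation rules need correcting in the same edit, because a contrast built on zeroed baselines and a raw-value responder would mislead.

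**What to change.** 1. **SAP 16.2:** restrict the rule that zeroes all pre-dose concentrations to the PK metrics, so that measured pre-dose glucose is kept for PD.
2. **SAP 16.1:** derive Inc20 as a rise of at least 20 mg/dL from pre-dose within 30 minutes, as the endpoint is worded in SAP section 15.
3. **SAP 16.4, continuous metrics:** for CEmax, AUE0-30 and AUE0-90 at Visits 2 and 4, report the dasiglucagon minus GlucaGen difference with a 95% CI and no p-value, from an ANCOVA with treatment and same-visit pre-dose glucose.
4. **SAP 16.4, responder:** report n (%) per arm and visit, with the difference and a score-type 95% CI (Newcombe or Miettinen-Nurminen).

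SAP 11.4 can stay as it is. The cost is two corrected derivations, some SAP text and a few table columns. No new data, sample size change or test is needed, and the descriptive status of the trial is preserved.

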17. STUDY DRUG ADMINISTRATION – EXTENT OF EXPOSURE

Analyses will be performed for the SAS population.

17.1 Extent of exposure

An overview table (not visit specific) will show information of derived summary parameters concerning study drug administration by treatment group:

- Total dose administered (summing up all successful dosing days including unscheduled dosing days (trial medication has been administered='yes')). dasiglucagon is administered in doses of 0.6mg per dosing day, GlucaGen® in doses of 1.0mg per administration.
- Number of days with IMP administration
- Total duration of exposure [weeks] (date of last exposure – date of first exposure + 1)

17.2 Time between visits and total study duration

Time between visits (unscheduled visits will not be displayed) as well as total study duration will be derived and tabulated with descriptive statistics (duration of total study (days) = date of study completion or discontinuation – date of informed consent + 1. Visit dates will be listed.

18. PROTOCOL DEVIATIONS

Protocol deviations as documented during the data review meeting will be listed.

19. COMMENTS

Comments if given will be listed.

20. CHANGES TO PROTOCOL-SPECIFIED ANALYSES

20.1 Changes to endpoints

N/A.

20.2 Changes to analyses

N/A.

21. APPENDICES

Appendix A: Presentation of Data and Programming Specifications

General

- Specialized text styles, such as bold, italics, borders, shading, superscripted and subscripted text will not be used in tables, figures, and data listings unless they add significant value to the table, figure, or data listing.
- Only standard keyboard characters are to be used in tables and data listings.
- Special characters, such as non-printable control characters, printer-specific, or font-specific characters, will not be used on a table, figure, or data listing.
- Hexadecimal character representations are allowed (e.g., μ , α , β).
- All footnotes will be left justified and at the bottom of a page. Footnotes should be used sparingly and must add value to the table, figure, or data listing.

Tables

- Titles will be left aligned.
- Formal organization of tabulations may be changed during programming if appropriate, e.g., tables for the different variables may be combined into a single table, or tables with more than one variable may be split into several tables.
- Means and medians will be presented to one more decimal place than the raw data. Standard deviations will be presented to two more decimal places than the raw data. Minimums and maximums will be reported with the same number of decimal places as the raw data.
- Percentages will be presented to the tenths place.
- For frequency counts of categorical variables, categories whose counts are zero will be displayed for the sake of completeness. For example, if none of the subjects discontinued due to “lost to follow-up,” this reason will be included in the table with a count of 0. Categories with zero counts will not have zero percentages displayed.
- Lower and upper confidence interval values should be presented to one decimal place more than the raw/derived data (i.e., to the same number of decimal places as the mean).
- Percentiles (e.g., 25%, 75%) should be presented to one decimal place more than the raw/derived data.
- For all inferential analyses, p-values will be rounded to four decimal places (or at the highest level of precision) with a leading zero (0.0001). P-values less than 0.0001 will be presented as “<0.0001”.

Figures

- Legends will be used for all figures with more than one variable or item displayed. Treatment group sizes (n=xx) will be included, as appropriate.
- Figures will be in black and white (no color) unless colors add value to the clarity and readability of a figure. Lines should be wide enough to see the line after being copied. Legends will be used for all figures with more than one variable or item displayed. Treatment group sizes (n=xx) will be included, as appropriate.
- Scatter plots will include the regression line if applicable.
- Line graphs over time of change from baseline results will include a horizontal dashed reference line at zero if requested/ specified.
- For box plots, the horizontal line will represent the median, + represents the group mean, the length of the box represents the interquartile range (25th-75th percentiles), and the whiskers will represent the minimum and maximum.

Listings

- Titles will be left aligned.
- Formal organization of the listing may be changed during programming if appropriate, e.g., additional variables may be included, change in the column order, or the listing may be split into multiple parts due to space constraints, etc.
- If not otherwise specified, all data listings will be sorted by treatment, patient number, visit, and date/time as appropriate.
- All date values will be presented in SAS date or ISO date format.
- All observed time values will be presented using a 24-hour clock HH:MM:SS format (e.g., 01:35:45 or 11:26). Seconds will only be reported if they were measured as part of the study.

Appendix B: SAS programming QC requirements

Programmer/ validator review

1. Program Review

- 1.1. **Program name** follows standard naming conventions and is consistent with other study program names.
- 1.2. **Program header** uses standard template with all relevant information completed.
- 1.3. **Program flow** is logical (i.e., header → initialization code → macro variable definitions → format definitions → main body).
- 1.4. **Programmer comments** are included throughout program to describe purpose of individual sections or macros and provide understanding of specific code, if necessary. All comments are clear and up-to-date.
- 1.5. **Hard coding**, if any, is implemented correctly and documented in program header with: date, reason, and reference to sponsor approval. A comment is also inserted at the location of the hard coding.
- 1.6. **SAP Derivation** rules, if any, are followed. Significant deviations from mock table or SAP text are documented in the SAS Program Header.
- 1.7. **Permanent intermediate datasets** utilized as source data have either been fully validated elsewhere or are fully validated within the scope of this QC .
- 1.8. **Endpoints** are generally derived in source datasets and not within the program itself.
- 1.9. **Program runs** properly and output dataset is generated as intended.

2. SAS Log Review

- 2.1. **Scan of entire log** confirming that each data step and procedure completed properly.
- 2.2. **Critical messages** such as: errors, warnings, merge notes, or uninitialized variables are not found in log. Unavoidable critical messages are verified to not adversely affect the output and the reasons why they are unavoidable are documented.
- 2.3. **Other messages** such as “PUT” or “INFO” messages (e.g., overwritten variables following merge) are handled appropriately, if they are found in log.

3. Output Review

- 3.1. **Output file name** follows standard naming conventions and is consistent with other study output file names.
- 3.2. **Titles and footnotes** are verified against mock figure (if available), corresponding table and/or SAP list of figures. Discrepancies, including

footnotes added for clarification or to match corresponding table, are noted and verified.

- 3.3. **Axis/legend labels** are verified against mock figure and/or corresponding table.
- 3.4. **Axis ranges** capture all available data and, if required, are consistent across other figures. Tick marks are spaced appropriately.
- 3.5. **Pages breaks** are as intended throughout the document.
- 3.6. **Inappropriate data**: checked for outliers, invalid numbers, missing results, etc.

4. Verification of Results

Verification of results may be performed using one of the following methods. The choice of QC method must be approved by the Biostatistics Project Lead.

- 4.1. Manual comparison to the corresponding table, where the table is validated and all data points on the figure are compared to the corresponding value on the table.
- 4.2. Independent confirmatory program is written to match output results.
- 4.3. Manual calculations (if feasible based on small Ns or frequency counts).
- 4.4. Manual comparison and program review, where the related table, if produced, is validated and a subset of data points are compared to the table. Program code and logs are reviewed to confirm the intended data is used appropriately throughout the program.
- 4.5. Study specific alternative method (if applicable) that is agreed upon by the sponsor and defined prospectively in a study specific document (e.g., Validation Plan, SAP or a modified QC requirement template TMP-SOP-0205-003).

5. Documentation

- 5.1 The Programmer and Validator must document completion of QC (e.g., date of QC and method used) in BIO-0205-TMP-002 Program Status Document.
- 5.2 Validator findings and/or comments may be tracked in the Program Status Document along with a description of how the finding was resolved and resolution date.
- 5.3 The following must be retained electronically within the study folder by the Programmer as supporting documentation for SDTM and TDM datasets:
 - Figure output generated at time of QC completion.
 - If comparison to corresponding validated table is performed, the corresponding table output that verifies results (Section 4.1).
 - If independent confirmatory program is created, a portion of the resulting output that verifies results (Section 4.2).

- 5.4** If manual calculations are performed, insert a comment into the output file to indicate verification of results (Section 4.3).

Senior Level Review

1. Output Package

- 1.1. All analysis tables, listings and figures**, as outlined in the SAP are contained in the package. If any are missing, the reason is documented appropriately.
- 1.2. Dates and times of electronic output files** are consistent with each other and with the corresponding dates of the source data sets.
- 1.3.** Output files are sorted in a user-friendly format such as by table, listing, and figure number. Table of Contents document is included to decode file names, or TLF number is included in the filename itself.

2. Database and Documentation

- 2.1. File dates of datasets** within the clinical database, SDTM datasets, and analysis datasets are consistent. All clinical database datasets were updated together at the appropriate time, SDTM datasets (if any) were updated following the update of the clinical database, and analysis datasets were updated following the update of the clinical source datasets and SDTM datasets (if any).
- 2.2. QC of all programs** has been completed by both the Programmer and Validator, as confirmed by **BIO-0205-TMP-002 Program Status Document**.
- 2.3. All datasets, SAS programs, and SAS program logs** have been saved and are ready for archival.
- 2.4. The randomization assignments** have been verified to be accurate in all datasets at the time of the final batch run of programs.

3. Output Review

- 3.1. Titles are appropriate** and match the corresponding mocks and Table of Contents (if available). Title format and numbering is consistent across all TLFs.
- 3.2. Footnotes are appropriate** and match the corresponding mocks and Table of Contents (if available). Reference numbers are consistent in format and correspond to the body of the output. Version of output is represented accordingly (e.g., DRAFT designation is removed, if final).
- 3.3. Formatting is consistent** across all analysis tables, listings, and figures (i.e., case/punctuation in column and row headers, underlining of column headers, page breaks, etc.).

- 3.4. Invalid data** such as blatant data point errors, outliers, missing data are scanned for in the outputs.
 - 3.5. Population denominators** are consistent across summary tables and figures.
 - 3.6. Potential discrepancies**, if any, found during review have been corrected and/or handled appropriately.
- 4. Statistical Review**
- 4.1. The primary efficacy analysis** and any key secondary efficacy or safety analyses are carefully reviewed for consistency and plausibility. Any potential issues are investigated and discussed with the Programmer and/or Biostatistician.

